9.3 Statistical Analysis

All analyses will be descriptive. Binomial variables will be presented as frequency and 95% CI. Continuous variables will be presented as median, mean, range, and 95% CI. Time-to-event endpoints will be analyzed according to the method of Kaplan-Meier.

Primary and exploratory analyses will be performed as described in detail in the study Statistical Analysis Plan.

9.3.1 *Efficacy Analysis Endpoints*

Efficacy endpoints include:

- Overall response rate (ORR), defined as the proportion of subjects with confirmed CR and PR according to the IWG criteria.
- Complete remission (CR) rate, defined as the proportion of subjects with confirmed CR (i.e., 2 CRs at least 28 days apart) according to the IWG criteria. Subjects who are not evaluable for response for any reason at or before the Cycle 6 response assessment will be considered as not achieving CR.
- Overall HI rate, defined as the proportion of subjects who demonstrate major hematologic improvement as defined by the IWG criteria. Only subjects with pre-treatment abnormal values will be considered for this endpoint at 8 weeks.
- Clinical benefit rate (CBR), defined as the proportion of subjects with confirmed CR, PR, Marrow CR, and HI. All patients who achieve hematologic CR, PR, marrow CR, or HI on the erythrocytic lineage (HI-E) per modified IWG response criteria will be considered responders.
- Rate of cytogenic complete response/remission, defined as the proportion of subjects with confirmed CR by cytogenetic assessment. Complete cytogenetic response is defined per modified IWG response criteria.
- Duration of response (DoR), for subjects who have achieved CR, PR, Marrow CR, or HI), defined as the time from the initial determination of response to the time of disease progression or death on study, whichever occurs first. For subjects who are alive and have not experienced disease progression on study (prior to receiving

subsequent/new treatment or stem cell transplant), duration of response will be censored at the day of the last disease assessment.

- Rate of leukemic transformation, defined as transformation at landmark time points of 6 months, 12 months, 18 months, and 24 months.
- Event-free survival (EFS), defined as the time from the first day of study drug administration (Day 1) to failure or death from any cause. Subjects who are alive and free from disease progression will be censored at the date of last disease assessment.

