Proposed Modified International Working Group Response Criteria for Altering Natural History of MDS	
Category	Response Criteria (responses must last at least 28 days)
Complete remission	
Bone marrow: $\leq 5\%$ myeloblasts with normal maturation of all cell lines*
 
Persistent dysplasia will be noted*†
 
Peripheral blood‡
 
Hemoglobin ≥ 11 g/dL
 
Platelets $\geq 100 \times 10^9/L$
 
Neutrophils $\geq 1.0 \times 10^9/L$†
 
Blasts 0%

Partial remission	
All CR criteria if abnormal before treatment except:
 
Bone marrow blasts decreased by $\geq 50\%$ over pretreatment but still $> 5\%$
 
Cellularity and morphology not relevant

Marrow CR†	
Bone marrow: $\leq 5\%$ myeloblasts and decrease by $\geq 50\%$ over pretreatment†
 
Peripheral blood: if HI responses, they will be noted in addition to marrow CR†

Stable disease	Failure to achieve at least PR, but no evidence of progression for > 8 weeks
Failure	Death during treatment or disease progression characterized by worsening of cytopenias, increase in percentage of bone marrow blasts, or progression to a more advanced MDS FAB subtype than pretreatment
Relapse after CR or PR	
At least 1 of the following:
 
Return to pretreatment bone marrow blast percentage
 
Decrement of $\geq 50\%$ from maximum remission/response levels in granulocytes or platelets
 
Reduction in hemoglobin concentration by ≥ 1.5 g/dL or transfusion dependence

Cytogenetic response	
Complete: Disappearance of the chromosomal abnormality without appearance of new ones
 
Partial: At least 50% reduction of the chromosomal abnormality

Disease progression	
For patients with:
 
Less than 5% blasts: $\geq 50\%$ increase in blasts to $> 5\%$ blasts
 
5% – 10% blasts: $\geq 50\%$ increase to $> 10\%$ blasts
 
10% – 20% blasts: $\geq 50\%$ increase to $> 20\%$ blasts
 
20% – 30% blasts: $\geq 50\%$ increase to $> 30\%$ blasts
 
Any of the following:
 
At least 50% decrement from maximum remission/response in granulocytes or platelets
 
Reduction in hemoglobin by ≥ 2 g/dL
 
Transfusion dependence

Survival	
Endpoints:
 
Overall: death from any cause
 
Event free: failure or death from any cause
 
PFS: disease progression or death from MDS
 
DFS: time to relapse
 
Cause-specific death: death related to MDS

Reference: [Cheson 2006](#).

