Abbreviations: CR = complete response; DFS = disease-free survival; FAB = French-American-British; MDS = myelodysplastic syndrome; PFS = progression-free survival; PR = partial response

Deletions to IWG response criteria are not shown. To convert hemoglobin from g/dL to g/L, multiply g/dL by 10.

* Dysplastic changes should consider the normal range of dysplastic changes (modification) ([Ramos et al. 1999](#))

† Modification to IWG response criteria.

‡ In some circumstances, protocol therapy may require the initiation of further treatment (e.g., consolidation, maintenance) before the 4-week period. Such patients can be included in the response category into which they fit at the time the therapy is started. Transient cytopenias during repeated chemotherapy courses should not be considered as interrupting durability of response, as long as they recover to the improved counts of the previous course.

Modified IWG Response Criteria for Hematological Improvement	
Hematological Improvement*	Response Criteria (responses must last at least 8 weeks) †
Erythroid response (pretreatment, < 11 g/dL) (HI-E)	Hemoglobin increase by ≥ 1.5 g/dL Relevant reduction of units of RBC transfusions by an absolute number of at least 4 RBC transfusions/8 weeks compared with the pretreatment transfusion number in the previous 8 weeks. Only RBC transfusions given for a hemoglobin of ≤ 9.0 g/dL pretreatment will count in the RBC transfusion response evaluation‡
Platelet response (pretreatment, < 100×10^9 /L) (HI-P)	Absolute increase of $\geq 30 \times 10^9$ /L for patients starting with $> 20 \times 10^9$ /L platelets Increase from $< 20 \times 10^9$ /L to $> 20 \times 10^9$ /L and by at least 100%†
Neutrophil response (pretreatment, < 1.0×10^9 /L) (HI-N)	At least 100% increase and an absolute increase $> 0.5 \times 10^9$ /L†
Progression or relapse after HI‡	At least 1 of the following: 
• At least 50% decrement from maximum response levels in granulocytes or platelets• Reduction in hemoglobin by ≥ 1.5 g/dL• Transfusion dependence

Abbreviations: HI = hematologic improvement; RBC = red blood cell;

Deletions to the IWG response criteria are not shown.

To convert hemoglobin levels from g/dL to g/L, multiply g/dL by 10.

* Pretreatment counts averages of at least 2 measurements (not influenced by transfusions) ≥ 1 week apart (modification).

† Modification to IWG response criteria.

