2.3.2 Secondary Endpoints

The secondary efficacy endpoints are:

- Complete remission (CR) rate: proportion of subjects with confirmed CR (i.e. 2 CRs at least 28 days apart) per IWG criteria. CR is defined as:
 - Bone marrow: $\leq 5\%$ myeloblasts with normal maturation of all cell lines; persistent dysplasia will be noted.
 - Peripheral blood (in the absence of transfusions)
 - Hemoglobin ≥ 11 g/dL
 - Platelets $\geq 100 \times 10^9/L$
 - Neutrophils $\geq 1.0 \times 10^9/L$
 - Blasts 0%
- Overall hematologic improvement (HI) rate: proportion of subjects who demonstrate major hematologic improvement per IWG criteria, for at least one criterion. Only subjects with pre-treatment abnormal values will be considered for this evaluation at 8 weeks.
- Clinical benefit rate (CBR): proportion of subjects with confirmed CR, PR, Marrow CR, or HI. All subjects who achieve hematologic CR, PR, marrow CR (with or without HI), or HI without marrow CR per IWG will be considered responders. PR is defined as all of the CR criteria if abnormal before treatment except bone marrow blasts, which can be decreased by $\geq 50\%$ over pretreatment but still $> 5\%$, and cellularity and morphology are not relevant. Marrow CR is defined, only in patients with MDS with excess blasts, as:
 - Bone marrow: $\leq 5\%$ myeloblasts and decrease by $\geq 50\%$ over pretreatment
 - Peripheral blood: if HI responses, they will be noted in addition to marrow CR
- Relapse: after CR or PR, at least one of:
 - Return to pretreatment bone marrow blast percentage

- Decrement of $\geq 50\%$ from maximum remission/response levels in granulocytes or platelets
 - Reduction in hemoglobin concentration by ≥ 1.5 g/dL or transfusion dependence
- Cytogenetic complete response/remission rate: proportion of subjects with disappearance of the chromosomal abnormality without appearance of new ones, by cytogenetic assessment in the subset of subjects with abnormal cytogenetics at baseline.
- Duration of response (DOR) will be derived in 2 ways: for subjects who achieve CR or PR (primary), and for subjects who achieve CR, PR, marrow CR or HI: time from initial determination of response to time of disease progression or death on study, whichever occurs first. For subjects who are alive and have not experienced disease progression on study (prior to receiving subsequent/new treatment or stem cell transplant), duration of response will be censored at the day of last disease assessment.

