- Leukemic transformation rate: leukemic transformation at landmark time points of 6, 12, 18, and 24 months.
- Event-free survival (EFS), defined as the time from the first day of study drug administration (Day 1) to disease progression, relapse or death from any cause. Subjects who are alive and free from disease progression will be censored at the date of last disease assessment .
- Progression-free survival (PFS): time from the first day of study drug administration (day 1) to progression per IWG criteria, or death on study. Subjects who are alive and free from disease progression will be censored at the date of last disease assessment.
- Overall survival (OS): time from the first day of study drug administration (day 1) to death from any cause on study. Subjects who are alive will be censored at the date of last visit or contact with the investigator.
- Time to Stem Cell Transplant (SCT): time from the first day of study drug administration (day 1) to SCT, for subjects with SCT. If no SCT date can be confirmed, SCT date will be imputed as study drug discontinuation day.

For each of DOR, EFS, PFS and OS, in the sensitivity analyses, subjects with no events who stopped treatment and received SCT will be censored at the SCT day (either confirmed SCT day, or study drug treatment discontinuation day, if no SCT date can be confirmed) even if there were events which occurred after the SCT date.

- For both stages, the rate of treatment discontinuation in the first 3 cycles of therapy due to possibly safety-related reasons will be used as a secondary endpoint to evaluate the safety and tolerability. Progressive disease and transplant are reasons to discontinuation related to efficacy, therefore these events will be excluded from the analysis. All the other reasons for treatment discontinuation will be considered as possibly safety-related, therefore will be included in the analysis as events.

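### Duration of response does not name relapse after CR or PR as an event, so a relapse that is not also IWG progression can be missed; separately, SAP PFS drops the protocol's recurrence component without declaring it

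*SAP*

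**What the plan says.** SAP 2.3.2 derives DOR for CR/PR responders (primary) and for a wider set that adds marrow CR and HI. Both run as the "time from initial determination of response to time of disease progression or death on study, whichever occurs first". Protocol 9.3.1 has the same event, running "from the initial determination of response to the time of disease progression or death on study, whichever occurs first". Responders who are alive and "have not experienced disease progression on study (prior to receiving subsequent/new treatment or stem cell transplant") are censored at the last disease assessment.

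Relapse after CR or PR is a separate concept in these documents. Protocol 5.2.4 lists it apart from disease progression as a response category, Appendix D gives the two different criteria, and SAP 2.3.2 restates the relapse criteria. SAP 2.3.2 also runs EFS "to disease progression, relapse or death from any cause", so relapse stands beside progression there. Protocol 4.3 puts both in one bullet, and either ends study treatment.

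On PFS, protocol 9.3.1 counts disease recurrence as well as progression and death. The SAP reads: "Progression-free survival (PFS): time from the first day of study drug administration (day 1) to progression per IWG criteria, or death on study". SAP Section 13 lists the change to OS censoring and the changes to the analysis populations, and nothing else.

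**The concern.** DOR should end when the response is lost. If a response ends in a relapse that does not also satisfy progression, the literal rule gives the subject no event at that point. Because relapse ends treatment, one of two things follows. The subject may be censored at the last disease assessment, which is informative censoring because it is tied to loss of response. Otherwise the subject counts as responding until a later progression or death. Neither route can shorten the recorded duration, so the bias is toward a longer DOR.

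A second route concerns data rather than criteria. Protocol 5.2.4 relies on investigator assessments, but the SAP does not say whether a DOR event is taken from the recorded category or re-derived from Appendix D. If it is taken from the category, a subject coded only as relapse has no DOR event even where the criteria overlap.

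SAP EFS would capture the relapse, but EFS runs from Day 1 and does not show how long responses last. For PFS, the events counted depend on which document is followed.

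**Working it through.** The plan gives no DOR median, event count or precision, so there is no figure to reproduce. The check compares definitions, then illustrates the size under stated assumptions.

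**1. Events by endpoint**

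| Endpoint | Source | Events |
|---|---|---|
| DOR | Protocol 9.3.1 | progression, death |
| DOR | SAP 2.3.2 | progression, death |
| EFS | SAP 2.3.2 | progression, relapse, death |
| PFS | Protocol 9.3.1 | recurrence, progression, death |
| PFS | SAP 2.3.2 | progression, death |

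**2. Relapse against progression (Appendix D)**

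| Component | Relapse after CR/PR | Progression | Relapse only |
|---|---|---|---|
| Granulocytes, platelets | fall of 50% or more from best level | "At least 50% decrement from maximum remission/response in granulocytes or platelets" | none |
| Transfusion dependence | yes | yes | none |
| Haemoglobin | fall of 1.5 g/dL or more | fall of 2 g/dL or more | 1.5 to under 2 g/dL |
| Marrow blasts | back to the pretreatment value | increase of 50% or more that also crosses a band limit | depends on the reference value |

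The haemoglobin gap is limited to sustained falls, because an Appendix D footnote says: "Transient cytopenias during repeated chemotherapy courses should not be considered as interrupting durability of response", provided counts recover.

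**3. Blasts.** Appendix D does not say what the 50% increase is measured from. I took whole-percent values, a response value of 1% or more, pretreatment blasts of 6% to 19%, and a return to exactly the pretreatment value.

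- Measured from the response value, CR: 5 response values (1% to 5%) × 14 pretreatment values = 70 pairs. For responses of 1% to 4%, all 4 × 14 = 56 meet progression. For a response of 5% (taken as the 5–10% band, which needs more than 10%), pretreatment 11% to 19% gives 9 that meet it and 6% to 10% gives 5 that do not. So 65 of 70 meet it.
- Measured from the response value, PR (response above 5% and at most half of pretreatment): 20 of 20 pairs meet it.
- Together, 85 of 90 meet progression and 5 of 90 do not.
- Measured from the pretreatment value, a return is a 0% increase, so none of the 90 meets progression.

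Fourteen pairs with a response value of 0% are left out because a 50% increase from zero is undefined. These are counts of value pairs, not patient frequencies.

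**4. Illustration of size.** Let f be the share of responses that end in a relapse that is not progression. No document gives f. Assume exponential times, relapse type independent of duration, and a true median m of 12 months. That is the pracinostat-arm median DoR quoted from MEI-003 in protocol 1.5, whose event definition is not given.

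- Event recorded d months late (assumed d = 3 or 6): median = m[1 + log2(1 − f + f·2^(d/m))]. For f = 10%, d = 3: 12 × [1 + log2(0.9 + 0.1 × 1.189)] = 12.3.
- Censored at relapse, treated as independent: m/(1 − f). For f = 10%: 12/0.9 = 13.3.
- Very long delay: m·log2[(1 − f)/(0.5 − f)]. For f = 10%: 12 × log2(2.25) = 14.0.

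| f | d = 3 to 6 months | Censored | Very long delay |
|---|---|---|---|
| 0 | 12.0 | 12.0 | 12.0 |
| 5% | 12.2 to 12.4 | 12.6 | 12.9 |
| 10% | 12.3 to 12.7 | 13.3 | 14.0 |
| 20% | 12.6 to 13.4 | 15.0 | 17.0 |

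**5. Against precision.** At the plan's 40% ORR, 0.40 × 60 = 24 responders, and f = 10% is about 2 of them. If all 24 had events, an exponential 95% interval around 12 months would be 12 × exp(±1.96/√24) = 8.0 to 17.9 months. The shift at f = 10% (0.3 to 2.0 months) lies well inside that.

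**The case against.** The best defence is that progression is used loosely as an umbrella term. SAP EFS counts relapse, yet its censoring rule speaks only of being free from progression; protocol PFS counts recurrence and does the same. Appendix D also merges progression and relapse after HI into one entry. On that reading relapse is already inside the DOR event. This shows the wording is unclear rather than that relapses will certainly be dropped. It does not remove the gap: the SAP defines relapse in the same section and names it for EFS but not for DOR.

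It is also fair that the residual is narrow. Since Appendix D measures count falls from the best response, the response value is a natural reference for blasts, which leaves 5 of 90 pairs. Some haemoglobin falls in the gap, such as 13.0 to 11.3 g/dL, still meet the CR threshold of 11 g/dL; they remain relapses by the documents' own rule, which carries no such limit.

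Several stronger inferences do not hold.

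- A reader might infer that the SAP departs from the protocol on DOR. It does not; the event is the same in both.
- A reader might take the absence of relapse from the best-response hierarchy in SAP 9.2.1 as support. It is none, because relapse follows CR or PR and can never be a best response.
- A reader might count returns to pretreatment blasts of 5% or less as missed losses of response. Such a marrow still meets the CR blast limit, and when pretreatment blasts are already that low the criterion can be met with almost no change.
- A reader might treat SAP PFS as plainly wrong. Its progression component matches Appendix D ("PFS: disease progression or death from MDS"), and recurrence is not an Appendix D category, so equating it with relapse is an inference. What stands is that the change is not declared.

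**Conclusion.** The concern holds in a bounded form. As written, DOR has no event for a relapse that is not also progression, and the resulting bias runs only toward longer DOR. The clear residual is sustained haemoglobin falls of 1.5 to under 2 g/dL and some or all returns to pretreatment blasts above 5%, depending on the unstated reference value. Subjects coded only as relapse are added if events come from the recorded category.

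The size cannot be derived from the documents. It is zero if every relapse also meets and is recorded as progression, and it is probably small against the precision from about 24 responders. The medians above illustrate assumed values of f; they do not show that DOR would be overstated by any particular amount. DOR and PFS are secondary and descriptive, and ORR is unaffected. The separate PFS point is an undeclared difference between protocol and SAP. Both should be corrected, but neither threatens the primary result.

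**What to change.** In SAP 2.3.2:

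- Define the DOR event for CR/PR responders as the earliest of IWG relapse after CR/PR, IWG progression, or death.
- For the wider responder set, also include the Appendix D entry for progression or relapse after HI. State how loss of marrow CR is handled, since Appendix D gives no relapse rule for it.
- State the reference value for the 50% blast increase.
- State that a return to pretreatment blasts that stays at 5% or less is not by itself a DOR event, and that the Appendix D transient-cytopenia footnote applies.
- State whether events come from the Appendix D criteria or from the investigator's recorded category.

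Record the DOR change in SAP Section 13. For PFS, either restore recurrence to match protocol 9.3.1, or keep progression only and declare and justify that in Section 13.

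The cost is a few sentences, the Section 13 entries and a small programming change. Blood counts, marrow results and transfusions are already collected. The reported DOR median, and possibly the PFS median, may be slightly shorter.

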3 STUDY DESIGN

3.1 Overall Study Design

This study is a two stage Phase 2 trial in subjects with IPSS-R high and very high risk myelodysplastic syndromes (MDS) previously untreated with hypomethylating agents.

Stage 1 is an open-label portion in approximately 40 evaluable subjects will be treated with pracinostat and azacitidine. The goal of Stage 1 is to evaluate treatment tolerability – based on whether the combination regimen of pracinostat and azacitidine’s rate of treatment discontinuation due to possibly safety reasons in the first 3 cycles of therapy is not significantly higher than 10%, and to determine if the observed efficacy justifies expansion of enrollment in Stage 1b based on ORR.

Stage 1b is an open-label expansion to achieve a total enrollment of approximately 60 subjects evaluable for efficacy, inclusive of Stage 1 and Stage 1b enrollment.

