9 STATISTICAL PLAN

9.1 Sample Size

Approximately 60 subjects evaluable for efficacy will be enrolled: approximately 40 in Stage 1 and 20 in Stage 1b. Non-evaluable subjects will be replaced.

9.1.1 *Sample Size Calculation for Stage 1*

The goal of Stage 1 is to establish if this pracinostat + azacitidine regimen achieves a discontinuation rate of approximately $\leq 10\%$ in the first 3 cycles of therapy, a rate comparable to that achieved in the azacitidine + placebo group in Study MEI-003. The 95% CI approach is utilized to estimate the sample size in Stage 1. The number of subjects to be enrolled is calculated such that the lower bound of the 95% CI of the discontinuation rate will be no more than 12% lower than the point estimate of 22.5%, the midpoint between the discontinuation rates in the azacitidine + placebo (10%) and azacitidine + pracinostat (32%) groups, respectively, in Study MEI-003.

With a sample size of 40 subjects, the study will be stopped if ≥ 9 subjects (22.5%, 95% CI: 10.8–38.4%) discontinue in the first 3 cycles. Under this scenario, the lower bound of the 95% CI is > 10 % (above the pre-specified desired goal) and the upper bound of the 95% CI is > 32 % (higher than the discontinuation rate in study MEI-003).

It is also possible to conclude that the desired threshold of a discontinuation rate of ≤ 10 % has been achieved with fewer than 40 subjects treated in Stage 1. For example, if 4 discontinuations are observed in the first 32 subjects, the lower and upper bounds of the 95% CI around the observed discontinuation rate of 12.5% (4 of 32) are 3.5% and 29.0%, lower than reported with azacitidine/placebo and azacitidine/pracinostat, respectively, in Study MEI-003. This would justify expanding enrollment to Stage 1b of the study after only 32 subjects have been treated for ≥ 3 cycles.

In addition to the discontinuation threshold, an observed ORR of ≥ 20 % will be desired to support opening Stage 1b of the study because it is expected that azacitidine alone results in an ORR of approximately 20% in high/very high-risk MDS.

The study's Independent Data Monitoring Committee (IDMC), in coordination with the Sponsor, will determine when enrollment in Stage 1 can be concluded, and whether to open enrollment in Stage 1b.

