4 SAMPLE SIZE CONSIDERATIONS

Approximately 60 subjects evaluable for efficacy will be enrolled: approximately 40 in Stage 1 and 20 in Stage 1b. Non-evaluable subjects will be replaced.

4.1 Sample Size Determination for Stage 1

The goal of Stage 1 is to establish if this pracinostat + azacitidine regimen is safe and tolerable, as measured by the rate of treatment discontinuation due to possibly safety related reasons in the first 3 cycles of therapy. An discontinuation rate of 10%, based on that was observed in the azacitidine + placebo group in Study MEI-003 will be used as the threshold for safety evaluation. The 95% CI approach is utilized to estimate the sample size in Stage 1. A rate of treatment discontinuation of 22.5%, the midpoint between the discontinuation rates in the azacitidine + placebo (10%) and azacitidine + pracinostat (32%) groups, respectively, in Study MEI-003, is assumed to be the estimated discontinuation rate due to possibly safety related reasons.

With a sample size of 40 subjects, the study will be stopped if ≥ 9 subjects (22.5%, 95% CI: 10.8–38.4%) discontinue in the first 3 cycles. Under this scenario, the lower bound of the 95% CI is $> 10\%$ (above the pre-specified desired goal).

In addition to the discontinuation threshold, the lower bound of 95% CI for an observed ORR of $\geq 25\%$ will be desired to support opening Stage 1b of the study because it is expected that azacitidine alone results in an ORR of approximately 25% in high/very high-risk MDS. For example, with a sample size of $N=40$ and an assumed ORR of 45% for the azacitidine + pracinostat combination regimen, the 95% CI using exact method is (29.3%, 61.5%) with the lower bound higher than 20%.

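### Failing to show a discontinuation rate above 10% does not establish tolerability: 8/40 meets the SAP's Stage 1 criterion with a 95% CI reaching 35.6%

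*SAP*

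**What the plan says.** **SAP.** Section 3.1 gives the Stage 1 goal as judging tolerability by whether the rate of "treatment discontinuation due to possibly safety reasons in the first 3 cycles of therapy is not significantly higher than 10"%. Section 4.1 fixes the reference: "An discontinuation rate of 10%, based on that was observed in the azacitidine + placebo group in Study MEI-003 will be used" as the safety threshold. It says that a rate of 22.5% "is assumed to be the estimated discontinuation rate due to possibly safety related reasons". Its only numerical rule is that, at 40 subjects, "the study will be stopped if ≥ 9 subjects (22.5%, 95% CI: 10.8–38.4%) discontinue in the first 3 cycles", because the lower limit is then above 10%. It sets no condition on the upper limit. Section 9.2 reports the 3-cycle rate with an exact binomial 95% CI, counting every reason for discontinuation except progression and transplant. Section 6.5 plans no formal hypothesis test.

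**Protocol.** Section 9.1.1 has the same 9/40 stop but adds that the upper limit then exceeds 32%, "higher than the discontinuation rate in study MEI-003". Sections 3 and 9.1.1 put the goal as a rate of approximately 10% or less. Section 9.1.1 and the synopsis continue: "It is also possible to conclude that the desired threshold of a discontinuation rate of" 10% or less is met before 40 subjects are treated. Their example is 4 of 32, where "the lower and upper bounds of the 95% CI around the observed discontinuation rate of 12.5% (4 of 32) are 3.5% and 29.0"%. These limits are said to lie below the MEI-003 placebo and pracinostat rates respectively.

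**Reference rate.** The protocol's sample-size text gives 32% for the MEI-003 pracinostat arm. Section 1.5 gives 26% for the first 3 cycles, excluding progression and transplant.

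**The concern.** A result that is not significantly above 10% can arise because the rate is low or because 40 subjects are too few to prove that it is high. The SAP criterion cannot tell these apart, yet section 4.1 says that Stage 1 is meant to establish that the regimen is safe and tolerable. The protocol attributes the lack of efficacy in MEI-003 to early discontinuation and runs this study to see whether a lower dose reduces it. The informative question is therefore whether the data exclude a rate as high as in MEI-003. The upper confidence limit answers that, and the SAP criterion does not use it.

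At stake is a statement on a primary objective, safety and tolerability, that the data at counts near the boundary would not support.

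**Working it through.** **Inputs.** N = 40, stop at 9 or more, reference 10%, assumed rate 22.5% (SAP 4.1). Exact binomial 95% CI (SAP 9.2). MEI-003 pracinostat rates of 26% (protocol 1.5) and 32% (protocol 9.1.1). Early example 4/32 (protocol 9.1.1).

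**Step 1: reproduce the plan's figures.** Clopper-Pearson limits for x of n are the 2.5% quantile of Beta(x, n − x + 1) and the 97.5% quantile of Beta(x + 1, n − x).

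- 9/40: 10.84% to 38.45%. The plan states 10.8% to 38.4%, so it reproduces to rounding.
- 4/32: 3.51% to 28.99%. The plan states 3.5% and 29.0%.

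**Step 2: where the SAP wording and the stop rule meet.** 8/40 has limits 9.05% and 35.65%. Its lower limit is below 10%, and that of 9/40 is above. So the section 3.1 wording and the 9/40 rule are the same rule, and 8/40 is the worst result that meets it. P(X ≥ 9 | 40, 10%) = 1.5%.

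**Step 3: what the counts that meet it can exclude.**

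| Count | Observed | Exact 95% CI | Upper limit below 32%? | Below 26%? |
|---|---|---|---|---|
| 4/40 | 10.0% | 2.8–23.7% | yes | yes |
| 5/40 | 12.5% | 4.2–26.8% | yes | no |
| 6/40 | 15.0% | 5.7–29.8% | yes | no |
| 7/40 | 17.5% | 7.3–32.8% | no | no |
| 8/40 | 20.0% | 9.1–35.6% | no | no |

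At 7/40 and 8/40 the upper limit already exceeds 32%, the feature that the protocol also mentions at 9/40, but the study does not stop.

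**Step 4: probability of meeting each criterion, P(X ≤ k | 40, p).** The SAP rule is k = 8. The columns k = 6 (upper limit below 32%) and k = 4 (upper limit below 26%, or an observed rate of at most 10%) are for comparison.

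| True rate | k = 8 (SAP) | k = 6 | k = 4 |
|---|---|---|---|
| 10% | 98.5% | 90.0% | 62.9% |
| 20% | 59.3% | 28.6% | 7.6% |
| 22.5% | 43.9% | 17.3% | 3.6% |
| 26% | 25.2% | 7.5% | 1.1% |
| 32% | 6.8% | 1.2% | 0.1% |

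The midpoint of 10% and 32% is (10 + 32)/2 = 21%, not 22.5%. At 21% the SAP rule is met 53.1% of the time.

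**Step 5: the 4/32 example.** The observed rate, 4/32 = 12.5%, is above 10%. The only limit below 10% is the lower one (3.5%), which shows that 10% is not excluded, not that it has been met. The upper limit, 29.0%, is below 32% but above 26%.

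**The case against.** **The protocol's go criterion is stricter.** Read as an observed rate, approximately 10% or less means 4/40 or fewer, which is met 3.6% of the time at a true 22.5%. This stands. Counts of 5 to 8 fall between the two documents' wordings, and reconciling them towards the protocol would remove the 44%. The SAP wording would still need correcting, because it governs how the result is judged.

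**44% is largely built in.** 22.5% is the stop boundary itself (9/40), and any cut-off is met roughly half the time when the true rate sits on it. This is fair. The figures at 26% and 32%, 25% and 7%, say more, and at 32% the rule stops the study 93% of the time.

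**Tolerability is not the only condition.** A reader might infer a 44% chance that a poorly tolerated regimen is expanded. The documents do not support that: Stage 1b also needs an ORR condition, IDMC advice and a sponsor decision. Nor is discontinuation uncapped; the observed count cannot exceed 8/40.

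**The 4/32 example does use the upper limit.** It compares 29.0% with the MEI-003 pracinostat rate. So it would pass an upper-limit test against 32%, and 4 is the most that would, since 5/32 has an upper limit of 32.8%. Only the stated conclusion about 10% is unsupported.

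**The plan is descriptive.** With no formal test planned and the exact CI reported, readers will see the upper limit. That softens the consequence, but it is also a reason not to rest the conclusion on non-significance.

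**Conclusion.** The point holds for the inference. SAP section 3.1 draws tolerability from a failure to show excess discontinuation, and results up to 8/40 meet that criterion while remaining compatible with both MEI-003 pracinostat rates. The chance of meeting it is 25% if the true rate is 26% and 7% if it is 32%. The conclusion attached to 4/32 in protocol section 9.1.1 and the synopsis is also unsupported as worded.

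The probabilities assume exactly 40 subjects (the plan says approximately 40), independent outcomes and the 9/40 boundary. They describe the tolerability condition alone.

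A reader might also infer that 6/40 or 4/40 should become the go limit. The documents do not settle that. The choice depends on an unreconciled 26% or 32% reference, it lowers the pass probability at a true 10% to 90% or 63%, and 6/40 would be looser than the protocol's 10% read as an observed rate. Those limits are illustrations only.

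**What to change.** 1. In SAP section 3.1, remove non-significance against 10% as the basis for concluding tolerability. In sections 3.1 and 4.1, describe 9 or more of 40 as a stop trigger only, and state that 8 or fewer is not by itself evidence of tolerability.
2. In protocol section 9.1.1 and the synopsis, replace the conclusion drawn from 4/32 with what the data show: an observed rate of 12.5%, with an upper limit of 29.0% that is below 32% but not below 26%.
3. Base any tolerability conclusion on the observed rate and the upper limit of the exact 95% CI already reported under SAP section 9.2, compared with the MEI-003 pracinostat rate once 26% and 32% are reconciled.
4. State the probabilities of meeting the criterion at true rates of 10%, 22.5%, 26% and 32%.
5. The sponsor should reconcile the protocol and SAP go criteria so that counts of 5 to 8 of 40 have one stated reading, and record any change in SAP section 13.

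The cost is wording only, with no added subjects or data. The downside is a less favourable stated conclusion at counts near the boundary.
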